## 4. Study Procedures

a. Study design, including the sequence and timing of study procedures (distinguish research procedures from those that are part of routine care).

Head-to-head Prospective Randomized Trial: At operation, consented patients will be randomized after removal of the DP specimen to either drain with a single closed suctioning Jackson Pratt versus a closed non-suctioning straight drain. Patients will be stratified based on the surgeon's assessment of the gland texture, as hard versus soft. All drains will be positioned near the pancreatic transection margin. Recorded variables at the time of surgery will include pancreatic gland texture, pancreatic duct diameter, blood loss, and intraoperative time.

Since both types of drains are currently used by surgeons at JHH, we believe that there is no significant change to what is considered routine care of these patients. Surgeon preference currently dictates the drain choice at the time of operation.

b. Study duration and number of study visits required of research participants.

Our plan is to randomize 134 pts per arm (268 total). Approximately 115 DPs are performed annually at JHH. Based on a patient recruitment rate of 90%, the estimated period to complete this trial will be 31 months.

The endpoints of the study are events noted in the 90-day postoperative period, therefore no additional study visits will be required for the study participants, other that their postoperative hospital stay and routine postoperative visits. A case report form (Appendices Section) will be used to facilitate routine collection of standardized information from every subject in order to reliably detect and grade POPF and other complications. This form will be completed by the study coordinator on the day of discharge +/- one day, on the day of re-discharge (in case of readmission) +/- one day, on the day of any postoperative outpatient visit +/- one day, and at 90 days from surgery +/- two weeks. This information will be collected either over the telephone.or in person (eg, in the hospital inpatient setting or at ordinary, outpatient, patient-care clinic visits).

c. Blinding, including justification for blinding or not blinding the trial, if applicable.

This will not be a blinded trial.

d. Justification of why participants will not receive routine care or will have current therapy stopped.

Participants in both groups will receive standard surgical and post-surgical care.

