## **Study Statistics**

a. Primary outcome variable.

The primary endpoints of the study will be the development of POPF, as recently defined and graded by the International Study Group of Pancreatic Surgery.

b. Secondary outcome variables.

Secondary endpoints will include length of hospital stay, need for enteral or parenteral nutrition, need for radiologic or surgical intervention, septic complications, and perioperative mortality.

c. Statistical plan including sample size justification and interim data analysis.

The incidence of either POPF after DP is approximately 30%, based on retrospective studies validating the ISGPS definition. A clinically significant reduction of the event rate to 15% in the treatment group would require enrollment of 134 patients per arm (268 total), assuming a 2-tailed test with  $\alpha$  of 0.05 and power of 0.80. We therefore plan to consent and enroll 300, accrue 270 (roughly 90% of 300).

Interim analysis will be performed after recruitment and analysis of 150 patients.

d. Early stopping rules.

The trial will be terminated prematurely, if statistically significant differences between the groups or potential safety risks are identified.

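### Endpoints run to day 90, but the final form may be completed from day 76, and no later check is required for every patient

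*Combined protocol and SAP*

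**What the plan says.** Section 4b (Study Procedures, study duration and visits) sets the period at risk: "The endpoints of the study are events noted in the 90-day postoperative period". It adds no study visits beyond the hospital stay and routine postoperative visits.

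The same section describes how events reach the data: "A case report form (Appendices Section) will be used to facilitate routine collection of standardized information from every subject". The form is completed around discharge, then "on the day of re-discharge (in case of readmission) +/- one day, on the day of any postoperative outpatient visit +/- one day", and finally "at 90 days from surgery +/- two weeks". On the mode of collection it says "This information will be collected either over the telephone" or in person.

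The Study Statistics section names POPF as the primary outcome. The secondary outcomes include "need for radiologic or surgical intervention, septic complications, and perioperative mortality", with no time limit other than the 90 days in section 4b.

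The case report form itself is in an appendix that is not part of the documents reviewed.

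**The concern.** The tolerance on the last scheduled form reaches back into the period that the form is meant to cover. The discharge, re-discharge and outpatient-visit forms each depend on the patient being in hospital or in clinic. Only the final form is tied to elapsed time since surgery, so it is the only one that reaches a patient who does not come back. If it is completed early, such a patient has no scheduled route into the data for the remaining days.

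The endpoints exposed are mainly the late secondary ones: a death outside hospital, or a septic complication or intervention managed at another hospital. At stake is complete capture of those events through day 90.

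**Working it through.** **Inputs**
- Endpoint period: 90 days after surgery (section 4b).
- Final form: day 90, two weeks either side (section 4b).
- Re-discharge and outpatient-visit forms: within one day of the event, no end date (section 4b).
- Sample size: 134 per arm for 30% versus 15%, two-sided alpha 0.05, power 0.80 (Study Statistics, item c).

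**Step 1. The plan's own figure.** The normal-approximation sample size for two proportions is

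n = [1.960 × √(2 × 0.225 × 0.775) + 0.842 × √(0.30 × 0.70 + 0.15 × 0.85)]² / 0.15² ≈ 120.5 per arm, or 121 rounded up.

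With the continuity correction, n' = (120.5 / 4) × [1 + √(1 + 4 / (120.5 × 0.15))]² ≈ 133.5, rounded up to 134. The stated figure reproduces. The form window is not among its inputs, so the sample size is not in question.

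**Step 2. Permitted days for the final form.** Earliest day: 90 − 14 = 76. Latest day: 90 + 14 = 104.

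**Step 3. Days left uncovered.** For a form on day d before day 90, the uncovered stretch is 90 − d days.

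| Final form on day | Days not covered by it | Share of 90 days |
|---|---|---|
| 76 | 14 | 14/90 = 15.6% |
| 83 | 7 | 7/90 = 7.8% |
| 89 | 1 | 1/90 = 1.1% |
| 90 to 104 | 0 | 0% |

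**Step 4. What the other forms cover in that stretch.**

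| Event between an early form and day 90 | Route into the data |
|---|---|
| Leads to a readmission known to the study team | Re-discharge form |
| Leads to an outpatient visit known to the study team | Outpatient-visit form |
| Death outside hospital, or care elsewhere, not known to the study team | None stated |

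Only the last row is a gap.

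**Step 5. Number of events.** This would need the share of final forms completed before day 90, the rate of endpoint events in the uncovered days, and the share of those events unknown to the study team. The documents give none of the three, so no count of missed events can be calculated.

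**The case against.** The strongest reply is that a symmetric window around a target day is an ordinary tolerance. The form is due at day 90, nothing suggests that completion will cluster early, and the re-discharge and visit forms continue regardless. Most of this stands, and it is why the point is minor. It does not remove the gap: a form on day 76 meets the protocol, and the event-driven forms do not reach a patient who never returns.

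The case report form or its instructions may also require a later check. That cannot be excluded, because the appendix was not available, so the point is made only about the text at hand.

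A reader might infer more than this, in three ways:
- **That nothing is checked after an early final form.** Section 4b does not support this, since the re-discharge and visit forms have no cut-off.
- **That about half the patients will be affected, because 14 of the 29 permitted days precede day 90.** This treats form dates as evenly spread, which the documents do not say. It would in any case count patients with uncovered days and not missed events.
- **That late forms will bring in events after day 90.** The definition in section 4b already excludes them, and whether events are dated is a matter for the unseen form.

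**Conclusion.** The point holds in a narrow form. The final form can be completed up to 14 days (15.6%) before the end of the 90-day endpoint period, and the available text requires no check on or after day 90 for every patient. The exposure is confined to patients with an early final form and an event before day 90 that brings no readmission or visit known to the study team.

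The effect on POPF is probably very small. That is a judgement: a fistula is likely to be noted during the hospital stay or at a visit, both of which trigger a form, but the documents give no event timing. A reader might infer a loss of power or a difference in ascertainment between arms. The documents support neither. They give no rate of missed events, and the window is the same in both arms.

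This is a cheap improvement of low severity.

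**What to change.** In section 4b, change the window of the final form from two weeks either side of day 90 to day 90 through day 104. Suggested wording: 'The final form is completed at 90 days from surgery, plus up to two weeks, by telephone or in person, and records events through day 90.'

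The maximum uncovered stretch then falls from 14 days to 0. Information from outpatient visits on days 76 to 89 is not lost, because the existing rule already requires a form at any such visit. Keeping the present window and repeating the check after every early form would also close the gap, but it adds a second contact for each of those patients.

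The cost is one line of protocol text, a window that narrows from 29 permitted days to 15, and some extra telephone calls for patients whose last routine visit falls before day 90. Telephone collection is already allowed. No study visit is added, and the sample size does not change.

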## 5. Inclusion/Exclusion Criteria

All patients undergoing DP at Johns Hopkins Hospital (except children < 18 years old, pregnant women, adults lacking capacity to consent, non-english-speakers, and prisoners),

irrespective of diagnosis, comorbidities, or administration of neoadjuvant therapy are eligible for this study.

## 6. Drugs/ Substances/ Devices

- a. The rationale for choosing the drug and dose or for choosing the device to be used.
- b. Justification and safety information if FDA approved drugs will be administered for non-FDA approved indications or if doses or routes of administration or participant populations are changed.
- c. Justification and safety information if non-FDA approved drugs without an IND will be administered.

This trial does not involve the use of a specific drug or device.

Date: 12-08-2012 Principal Investigator: [name] Application Number: NA\_00080937

## **Study Statistics**

a. Primary outcome variable.

The primary endpoints of the study will be the development of POPF, as recently defined and graded by the International Study Group of Pancreatic Surgery.

b. Secondary outcome variables.

Secondary endpoints will include length of hospital stay, need for enteral or parenteral nutrition, need for radiologic or surgical intervention, septic complications, and perioperative mortality.

c. Statistical plan including sample size justification and interim data analysis.

The incidence of either POPF after DP is approximately 30%, based on retrospective studies validating the ISGPS definition. A clinically significant reduction of the event rate to 15% in the treatment group would require enrollment of 134 patients per arm (268 total), assuming a 2-tailed test with  $\alpha$  of 0.05 and power of 0.80. We therefore plan to consent and enroll 300, accrue 270 (roughly 90% of 300).

Interim analysis will be performed after recruitment and analysis of 150 patients.

d. Early stopping rules.

The trial will be terminated prematurely, if statistically significant differences between the groups or potential safety risks are identified.

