e. Justification for inclusion of a placebo or non-treatment group.

Both study groups will receive standard treatment (DP) for their pancreatic pathology.

f. Definition of treatment failure or participant removal criteria.

Treatment failure is defined as the development of any condition that poses identifiable risk to participant safety, or the incidence of POPF at significantly higher rate that the control group.

g. Description of what happens to participants receiving therapy when study ends or if a participant's participation in the study ends prematurely.

Patients will continue to receive standard post-operative care if their participation in the study ends prematurely, or after the study ends.

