## 7. Risks

a. Medical risks, listing all procedures, their major and minor risks and expected frequency.

This research adds no additional risk to a patient undergoing a DP. Patients will be randomized to one of two widely accepted drainage techniques. If in the opinion of the surgeon at the time of surgery, one technique has a perceived advantage over the other, that patient will undergo the technique felt to be indicated.

Therefore, medical risks are those of DP: bleeding, infection, anesthesia risks, fistula formation, pain, stroke, death, myocardial infarction, non-healing wound, diabetes mellitus, need for reoperation.

b. Steps taken to minimize the risks.

Preoperative anesthesia evaluation, cardiology clearance when necessary, optimization of the management of patient's comorbities, perioperative antibiotic prophylaxis, perioperative and postoperative pain control, nutritional support.

c. Plan for reporting unanticipated problems or study deviations.

The principal investigator will monitor patient safety and care. Adverse events or unanticipated problems will be reported in the Department of Surgery monthly research meeting. Necessary changes to the study protocol will be made on an as needed basis.

This is a Level I study under the SKCCC Data and Safety Monitoring Plan. The SKCCC Clinical Research Office Quality Assurance Group will perform periodic audits on this study. All trial monitoring and reporting will be reviewed annually by the SKCCC Safety Monitoring Committee.

d. Legal risks such as the risks that would be associated with breach of confidentiality.

Participants will be required to sign an informed consent in order to enroll in this study. The privacy and confidentiality of the patients in this study will be preserved in the standards of HIPAA and privacy policy of the Johns Hopkins Hospital. All de-identified protected health information will be saved in password-protected hospital computer drives. Access to data collected in this study will be limited to the research team members. If a patient's confidentiality is accidentally breeched, the patient will be notified by the principal investigator and measures will be taken to rectify such events.

e. Financial risks to the participants.

Monetary risks are similar to those for any patient undergoing DP. This includes the cost of surgery and rehabilitation, time off from employment, and adjuvant therapy if indicated.

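### The early-stopping rule gives no interim level, boundary, adjusted final level or test, and using 0.05 at both looks would not preserve the stated 0.05

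*Combined protocol and SAP*

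**What the plan says.** Study Statistics, item c, sets the sample size: a fall in POPF from 30% to 15% "would require enrollment of 134 patients per arm (268 total), assuming a 2-tailed test with" α of 0.05 and power 0.80. The same item adds one look: "Interim analysis will be performed after recruitment and analysis of 150 patients". Item d is a single sentence: "The trial will be terminated prematurely, if statistically significant differences between the groups or potential safety risks are identified".

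Two other places touch on the matter without supplying a boundary. Section 4f includes in its definition of treatment failure "the incidence of POPF at significantly higher rate that the control group", with no level or timing and no link to Study Statistics. Section 7c refers to an institutional monitoring plan and states: "All trial monitoring and reporting will be reviewed annually by the SKCCC Safety Monitoring Committee".

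**The concern.** The 0.05 is attached to the sample size for one test, yet the plan allows two chances to declare a difference. Nothing says how the 0.05 is shared between them, which test is used, or that the stop is judged on POPF. POPF is the natural reading, but item d does not say so. Nor does it mention the 150-patient look, which comes from item c.

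Three things are at stake.

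- **The decision itself.** The wording is mandatory, but the criterion is undefined, so the same interim data could end the trial or not. The trial is unblinded (section 4c) and the principal investigator monitors safety (section 7c), so a criterion settled after the data are seen would be hard to defend.
- **The false-positive rate.** If 0.05 is used twice, the overall rate exceeds 0.05.
- **The estimate.** Trials stopped at an interim look tend, on average, to overstate the difference.

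**Working it through.** **Inputs from the plan.** POPF 30% against 15%; two-sided 0.05; power 0.80; 134 per arm (268 total), with 270 (135 per arm) as the accrual target; one look at 150. From section 4b: 115 operations a year, 90% recruitment, 90-day endpoints.

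**Assumptions.** 0.05 at both looks; POPF only; 75 per arm at the look; common null event rates from 15% to 30%.

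**1. The plan's own figure.** With mean rate 0.225:

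n = [1.960·√(2×0.225×0.775) + 0.842·√(0.30×0.70 + 0.15×0.85)]² / 0.15² = 120.5, so 121 per arm uncorrected.

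With continuity correction: (120.5/4)·[1 + √(1 + 4/(120.5×0.15))]² = 133.5, so 134 per arm. The stated figure is reproduced, but only with the correction.

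**2. Type I error with 0.05 at both looks.** The test is z = (|difference| − c)/√(2p(1−p)/n), where p is the pooled rate and n the number per arm; c = 0 (uncorrected) or 1/n (corrected). All outcomes at 75 per arm, then at 134, were enumerated with exact binomial probabilities.

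| Null rate | Corrected, one look | Corrected, two looks | Uncorrected, one look | Uncorrected, two looks |
|---|---|---|---|---|
| 15% | 0.0341 | 0.0526 | 0.0495 | 0.0816 |
| 20% | 0.0346 | 0.0540 | 0.0507 | 0.0822 |
| 22.5% | 0.0348 | 0.0549 | 0.0509 | 0.0816 |
| 25% | 0.0353 | 0.0558 | 0.0508 | 0.0813 |
| 30% | 0.0369 | 0.0573 | 0.0505 | 0.0804 |

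With 135 per arm the corrected two-look range is 0.0517–0.0569, and the uncorrected error reaches at most 0.0826. Normal theory, with correlation √(150/268) = 0.748 between looks, gives 0.0811. The extra look adds about 2 points (corrected) or 3 points (uncorrected).

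**3. How often the boundary decides, at 30% against 15%.** Two standard boundaries serve as comparators: a Lan-DeMets O'Brien-Fleming-type boundary spending 0.025 per side (interim p<0.0055, final p<0.048) and Haybittle-Peto (interim p<0.001, final p<0.0498). Entries are uncorrected / corrected.

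| Rule | Stop at 150 | Power | Mean difference at a stop (points) |
|---|---|---|---|
| Single final test | – | 0.847 / 0.806 | – |
| 0.05 at both looks | 0.601 / 0.527 | 0.864 / 0.824 | 19.3 / 20.0 |
| O'Brien-Fleming-type | 0.282 / 0.212 | 0.843 / 0.804 | 22.9 / 24.1 |
| Haybittle-Peto | 0.125 / 0.093 | 0.847 / 0.806 | 25.9 / 26.8 |

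- p between 0.05 and 0.0055: 0.601 − 0.282 = 0.319 uncorrected; 0.527 − 0.212 = 0.315 corrected.
- p between 0.05 and 0.001: 0.601 − 0.125 = 0.476 uncorrected; 0.527 − 0.093 = 0.434 corrected.
- The true difference is 15 points. Among stops at 0.05, 20% (uncorrected) or 9% (corrected) still show 15 points or less.

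**4. Two concrete interim results (events out of 75 per arm).**

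- 22 against 10: p = 0.017 uncorrected, 0.028 corrected. This stops at 0.05 but not at 0.0055 or 0.001.
- 23 against 12: pooled rate 35/150 = 0.233, standard error 0.0691. Uncorrected z = 0.1467/0.0691 = 2.12, p = 0.034; corrected z = 0.1333/0.0691 = 1.93, p = 0.054. The choice of test alone decides. The two tests disagree about stopping at 0.05 in 7.5% of trials.

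**The case against.** The strongest reply is that the error inflation is conditional and may be slight. No sentence says 0.05 applies at the interim, and only the corrected test is consistent with 134 per arm. On that test the excess over 0.05 is 0.2 to 0.7 points. This stands, and type I error is therefore not the main ground for the concern. But the plan names no test, so the 0.08 figure cannot be excluded, and if a level other than 0.05 was meant, it is still unwritten.

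Second, the 32% and 43–48% figures depend on strict comparators. Against a Pocock-type boundary (about 0.030 at both looks), roughly 9% of trials would fall in the gap. That is correct. The spread from 9% to 48% across accepted boundaries also shows how much is left open.

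Third, the example boundaries are conservative with the corrected test: actual error is 0.032–0.037, about that of the fixed design. Using 0.045 at both looks with that test would give 0.044–0.050, power 0.813 and a stop probability of 0.51. So much of the loss of early stops comes from the boundary chosen rather than from error control as such. This is a fair point about which boundary to choose; it does not supply the missing one.

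Fourth, the overestimate looks smaller when averaged over all trials rather than stopped ones: 16.1–16.2 points with 0.05 at both looks, against 15.5–16.0 with the stricter boundaries. This also stands. Stricter boundaries reduce the overall bias, but not the overestimate in a trial that does stop.

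**Conclusion.** The concern holds. The document contains a mandatory stopping rule with no interim level, boundary, adjusted final level, test or named endpoint, and sections 4f and 7c do not fill the gap. The chief defect is that the rule cannot be applied as written.

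The second is that the only stated level, used at both looks, does not preserve 0.05: the excess is under 1 point with the design-matching test and about 3 points with an uncorrected one. These sizes rest on the assumptions listed above. Item d does not exclude stopping on secondary endpoints or at further looks, and either would raise the error further.

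**What to change.** Before the 150-patient look, amend Study Statistics c and d to do the following.

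- State that efficacy stopping uses POPF only, at the one look at 150 patients.
- Name the test, for example the continuity-corrected test that matches 134 per arm.
- Adopt one boundary with its final level. Examples are Haybittle-Peto (0.001, then 0.0498) or the O'Brien-Fleming-type boundary (0.0055, then 0.048). State the spending convention for the latter: the same function applied to 0.05 two-sided gives 0.0088 and 0.0466.
- Say whether accrual continues while the 150 complete follow-up, since "The endpoints of the study are events noted in the 90-day postoperative period".
- Keep safety stopping as a separate rule, and reconcile the wording of section 4f with Study Statistics.
- If the trial stops early, report an estimate and interval that allow for the stop.

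**Cost.** The change is to wording, and maximum sample size does not rise. Power under either example is 0.804–0.806 corrected (0.843–0.847 uncorrected), against 0.806 (0.847) for the fixed design and 0.824 (0.864) for 0.05 used twice.

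The real cost is fewer early stops, and so more patients on average if the effect is as designed. If accrual halts at 150, expected enrolment is 150s + 268(1 − s), where s is the stop probability. With 0.05 twice and the corrected test, 150×0.527 + 268×0.473 = 206. Over both tests, expected enrolment rises from 197–206 to 235–243 (O'Brien-Fleming-type) or 253–257 (Haybittle-Peto).

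If accrual continues, 115×0.90 = 103.5 a year gives 103.5×90/365.25 = 25.5 more patients in 90 days, so a stop counts as 176. The figures become 213–220, rising to 242–249 or 256–259. The increase is thus about 29 to 56 patients, or roughly 3 to 6 months at 103.5 a year.
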